2.3. Benefit/Risk Assessment

As indicated above, anti-PD-1 monoclonal antibody nivolumab was recently approved by the FDA for the treatment of melanoma in the adjuvant setting based on improvement in RFS in a randomized, double-blind study CHECKMATE-238. The most common adverse reactions in the study (reported in at least 20% of nivolumab-treated subjects) were fatigue, diarrhea, rash, musculoskeletal pain, pruritus, headache, nausea, upper respiratory infection, and abdominal pain. The most common immune-mediated adverse reactions were rash (16%), diarrhea/colitis (6%), and hepatitis (3%). For information about the known and expected benefits and risks and reasonably expected AEs of nivolumab refer to the Package Insert ([OPDIVO®, 2018](#)).

Anti-tumor activity of intratumoral tavo-EP demonstrated that intratumoral tavo-EP leads to significant increases in intratumoral IL-12 concentration without systemic IL-12 exposure, or systemic immune-related toxicities. Moreover, intratumoral tavo-EP in melanoma has been shown to not only increase intratumoral expression of IL-12 but also genes related to innate immunity, antigen presentation and anti-tumor adaptive immune responses. Efficacy data with tavo-EP in combination with anti-PD-1 monoclonal antibody pembrolizumab (OMS-I102) in subjects with melanoma that has low tumor infiltrating lymphocytes (TILs) showed a BORR of 50% (11/22); a CR of 41% (9/22); a disease control rate (DCR; CR + PR + stable disease [SD]) of 59% (13/22); progression free survival (PFS) of 57% at 15 months; and duration of response (DOR) of 100% (11/11) ([Algazi, 2016](#); [Algazi, 2016 AACR](#); [Algazi, 2017](#)).

The most frequently reported treatment-related adverse event (AE) is transient pain in association with the EP procedure. Other common treatment-related AE (incidence of $\geq 10\%$ of subjects) treated with intratumoral tavo-EP as monotherapy were pain, injection site inflammation and injection site discoloration, most of which have been Grade 1 or 2 in severity. One tavo-EP monotherapy subject experienced a treatment-related serious adverse drug reaction (ADR), a Grade 3 cellulitis and 1 subject died due to tumor hemorrhage assessed by the

Investigator as unlikely related to study treatment. Two monotherapy subjects discontinued the study due to treatment related procedural pain.

For the combination therapy study (tavo-EP with pembrolizumab; CC-15852/OMS-I102), the common study treatment-related TEAEs (incidence of >10%) were fatigue, dizziness, myalgia, injection site pain, pruritus, nausea, procedural pain, arthralgia, and diarrhea, all of which have been Grade 1 or 2. No deaths have been reported among subjects. One subject reported a Grade 3 cellulitis assessed by the investigator as related to tavo-EP and unlikely related to pembrolizumab. Two subjects discontinued treatment due to AE; 1 subject experienced Grade 2 diarrhea, assessed by the investigator as not related to tavo-EP and possibly related to pembrolizumab; 1 subject experienced 2 AEs, a Grade 2 confusional state assessed by the investigator as possible related to tavo-EP and pembrolizumab, and a Grade 1 paresthesia, assessed by the investigator as not related to tavo-EP and pembrolizumab.

Most subjects report discomfort and/or pain associated with EP, even with administration of local anesthesia, oral pain killers, and anxiolytics. The BP-associated pain, described as an "electrical shock" or "sharp punch" is experienced only during administration of the EP pulses and is transient. It is recommended that the area be iced or treated with a topical numbing agent. Individuals should be properly informed to prepare for the EP discomfort and pain sensation before treatment in procedures where general anesthesia is not indicated or desired. For subjects with low pain thresholds or with large treatment areas requiring multiple EPs, the subject may receive Ativan (Iorazepam) as prophylaxis.

More detailed information about the known and expected benefits and risks and reasonably expected AEs of intratumoral tavo-EP may be found in the IB.

3. OBJECTIVES AND ENDPOINTS

Objectives	Endpoints
Primary	

 To assess the complete pCR of intratumoral tavo-EP in combination with IV nivolumab (collectively 'the combined treatment') in subjects with operable locally-regionally advanced melanoma. 	
 pCR defined as proportion of subjects with no viable tumor on histologic assessment at definitive surgery.
Secondary	

 To assess 
 (a) radiologic/clinical preoperative response rate, (b) RFS and (c) OS. 	
 ORR assessed by Investigator based on RECIST v1.1 at 12 weeks during the Neoadjuvant phase (preoperative, unconfirmed). Duration of response (DOR) RFS iBORR assessed by Investigator based on iRECIST (optional). OS

 To assess safety and tolerability of the combined treatment as neoadjuvant therapy in subjects with operable locally-regionally advanced melanoma. 	
 Frequency, duration and severity of AEs and SAEs. Number of subjects with ECIs. Number of subjects who discontinued due to AEs. Incidence and shifts of clinically significant laboratory abnormalities; safety laboratory evaluations includes CBC, blood biochemistry and urinalysis.

 To assess the risk of surgical delay (either due to toxicity and/or tumor progression). 	
 Definitive surgery will be planned at about 12 weeks. Patients will be monitored for surgical delay (either due to toxicity and/or tumor progression).
Exploratory	

 Immune monitoring. 	
 Characterization of the tumor microenvironment and assessment of

Objectives	Endpoints
	immune phenotypes and function associated with treatment

4. STUDY DESIGN

4.1. Overall Design

This will be a Phase 2, Simon 2 stage minimax, open-label, single-arm study of neoadjuvant treatment of intratumoral tavo-EP plus nivolumab IV. Eligible subjects will be those with pathological diagnosis of operable locally-regionally advanced melanoma. The purpose and procedures of the study will be fully explained to potential subjects. Those wishing to enroll in the study will sign a written informed consent prior to initiating any study-related evaluations or procedures. Screening must be completed within 28 days prior to initiation of the study treatment (i.e. Cycle 1 Day 1; C1D1).

The Treatment period will be comprised of 3 phases:

Neoadjuvant Phase (Up to 3 x 4-week cycles, total 12 weeks): At every cycle, intratumoral tavo-EP will be administered (on Days 1 and 8) concurrently with 480 mg nivolumab IV infusion on Day 8 of each cycle (tavo-EP will be administered prior to nivolumab infusion).

Definitive Surgery Phase: Surgery may be scheduled about 2-4 weeks after the last dose of nivolumab following radiologic and clinical assessment at that point. Pathologic response will be determined by institutional pathologist. Refer to Appendix 8 (Section 10.8) for suggested guidelines on surgical management and techniques. These are important standard of care surgical guidelines and all investigators are strongly urged to consider them in the management of their patients. Under certain circumstances, the definitive surgery may be delayed and done after completion of additional cycles of neoadjuvant therapy if perceived by the treating physician investigators (surgeon and medical oncologist) to be in the best interest of the patient (or earlier if study intervention(s) was discontinued due to AEs or other reasons).

Adjuvant Phase: Adjuvant therapy with nivolumab monotherapy will begin approximately 2-4 weeks following definitive surgery; recovery from surgery is required (Day 1 of Cycle 4 will be determined by the treating investigator once the subject is cleared to initiate systemic therapy). Nivolumab (480 mg IV infusion on Day 1 of each 4-week cycle) will be administered for up to 9 cycles during the Adjuvant phase.

In Simon minimax Stage 1, up to 22 subjects can be enrolled. If the number of responders in Stage 1 meet the pre-specified number ($N \geq 3 // 22$), enrollment for Stage 2 will include an additional 11 subjects (for a total of 33 subjects).

All subjects will be followed for 4 weeks after last dose of nivolumab at EOS visit; data from standard of care imaging will be captured (every 3 months for 2 years post-surgery and every 6 months thereafter for up to 3 years post-surgery); long-term survival status will be determined every 6 month (by phone) for up to 5 years unless the study is terminated early.

Written IND safety reports will be submitted to the FDA by the IND sponsor, for serious, unexpected suspected adverse reactions within 15 calendar days of learning of its occurrence. If the event is fatal or is deemed to be life threatening, the report will be made within 7 calendar days. The IND sponsor will also make an assessment of whether the event constitutes an unanticipated problem posing risks to subjects or others (UP). This assessment will be provided to the IRB, which, in turn will make a final determination. If the IRB determines an event is a UP it will notify the appropriate regulatory agencies and institutional officials.

4.2. Scientific Rationale for Study Design

Pooled data from 4 ongoing neoadjuvant therapy studies at 3 large melanoma centers participating in the International Neoadjuvant Melanoma Consortium indicated that neoadjuvant targeted and immunotherapy are associated with a high pCR rate in stage III melanoma (Tetzlaff, 2018). Preliminary data suggest pCR correlates with improved RFS, particularly in those with pCR with immunotherapy (Menzies, 2017). Neoadjuvant evaluation of anti-PD-1 agent nivolumab in combination with tavo may improve the clinical outcome in subjects with advanced operable melanoma as it can transform poorly infiltrated/non-inflamed tumors into immunologically active lesions. The response rate (both pathologic and radiologic) in this setting is important to define to guide the field on the best approach for managing clinically evident operable disease. It will also provide needed data that would guide future nivolumab-based active combinations that may have important applicability in this setting.

The pCR rate (defined as no viable tumor on histologic assessment at surgery) is the most clinically meaningful endpoint with this immunotherapeutic agent given the implications on both the operability of the disease and on survival. The preoperative radiologic response rate will also be informative and clinically meaningful and such responses are expected to translate into durable survival benefits based on the current experience with nivolumab.

4.3. Justification for Dose

4.3.1. Tavo Dose Selection Rationale

Dose: Phase 1 clinical study to evaluate the safety and efficacy of a single cycle of intratumoral tavo-EP as a monotherapy in subjects with unresectable or metastatic melanoma showed 19 of 24 (79%) subjects enrolled on this study had additional sites of disease outside of the treated lesions (distant disease), and these subjects were therefore evaluated for distant response to therapy. In 53% there was evidence of a systemic response resulting in either stable disease, or objective regression of untreated lesions. In addition, in 3/19 subjects (15%) all of the distant lesions regressed completely in either the absence of any other systemic antitumor therapy (n=2) or following treatment with dacarbazine (n=1). Thus, the tavo selected dose (concentration of 0.5 mg/mL at a dose volume of approximately ¼ of the calculated lesion volume) is based on the dose cohort that yielded the highest proportion of responders.

Intratumoral administration: Systemic administration of IL-12 in multiple clinical studies in recombinant form (Atkins, 1997; Leonard, 1997; Hurteau, 2001) or via IL-12-expressing adoptive cell therapies (Rosenberg, 2015; National Cancer Institute, 2017) led to widespread, severe immune-related toxicities and death, but little or no anti-cancer efficacy in nearly all solid tumor indications.

To mitigate these toxicities, a multitude of localized delivery approaches have been explored (Sangro, 2004; van Herpen, 2004; Heinzerling, 2005; Mahvi, 2007; Anwer, 2010; Anwer, 2013; Linette, 2013; Nemunaitis, 2013; Nemunaitis, 2014; Lebel, 2015; Lebel, 2016; 2016; McArthur, 2016). The best efficacy demonstrated to date by any of these approaches was 20-50% ORR; these responses were accompanied by systemic Grade 3 or higher drug-related SAEs in 16-50%

of subjects across all indications tested (Linette, 2013; Nemunaitis, 2013; Nemunaitis, 2014; Lebel, 2015; Lebel, 2016; 2016; McArthur, 2016). In all studies where significant IL-12-related efficacy was achieved, related toxicities led to removal of at least some subjects from therapy or, in several cases, halt of the studies (Atkins, 1997; Leonard, 1997; Hurteau, 2001; Heinzerling, 2005; Mahvi, 2007; Anwer, 2010; Rudman, 2011; Anwer, 2013; Linette, 2013; Nemunaitis, 2013; Nemunaitis, 2014; Lebel, 2015; Rosenberg, 2015; Lebel, 2016; 2016; McArthur, 2016; National Cancer Institute, 2017).

As a monotherapy in advanced melanoma, ImmunoPulse® tavo yielded 33% best ORR, with 62% of subjects showing regression of untreated lesions (Daud, 2014; Daud, 2014). Yet, in contrast to other monotherapies yielding comparable objective responses (Nemunaitis, 2013; Nemunaitis, 2014; KEYTRUDA®, 2015; Lebel, 2015; Lebel, 2016; 2016; McArthur, 2016; OPDIVO®, 2018), ImmunoPulse® tavo treatment has not resulted in any systemic drug-related SAEs (Daud, 2008; Daud, 2014; Daud, 2014; Pierce, 2014; Bhatia, 2015; Pierce, 2015).

Regimen: Assessment of treatment on Days 1 and 8 at 4-week intervals will be evaluated in this study in neoadjuvant settings. Since IL-12 has an estimated half-life of 2-12 hours (Atkins, 1997; Portielje, 2005; Arkenau, 2011; Bhatia, 2015), any IL-12 that may enter the systemic circulation would be cleared within the 4-week cycle duration, and thus, cumulative increases in IL-12 should not be of concern when applying a 4-week cycle frequency with tavo and EP for co-localization of placement.

4.3.2. Electroporation Parameters Rationale

Of the methods available for in vivo gene delivery, EP is associated with high transfection efficiency and is a clinically developed platform (Potter, 2003).

Exposure of cells or tissue to brief, controlled electrical pulses at a specified electrical voltage causes a transient increase in cell membrane permeability, allowing macromolecules such as DNA to enter the cell and be expressed (i.e., transfection) (Gehl, 2003). EP-mediated transfection with plasmid DNA (pDNA) represents a non-viral gene therapy. EP has been used extensively to deliver pDNA to cartilage, blood, muscle, epithelial and loose connective tissue (Grossin, 2003; Weissinger, 2003; Kunieda, 2004; Hirao, 2008; Yuan, 2008). EP has also been applied to tumors to enhance the uptake of immunomodulatory genes (Lohr, 2001; Yamashita, 2001; Li, 2002; Lucas, 2002).

Electrical conditions utilized for electrochemotherapy have historically been used to deliver immunomodulatory genes to tumor tissues (Lucas, 2002). The reasoning behind this is the short-duration high-intensity pulses result in less tissue damage and fewer muscle contractions than traditional long-duration lower-intensity gene therapy conditions (Arena, 2012). Ultimately, using these pulses results in a shorter duration of expression, which is inconsequential as activation of the immune system results in the eventual destruction of transfected tumor cells. Commonly, this has resulted in the use of 6 pulses at a field strength (E+) of 1500 volt/cm and pulse width of 100 μ s at 300 msec intervals, which are the parameters used by the OMS system.

4.3.3. Nivolumab Dose Selection Rationale

Nivolumab will be administered according to the approved label. The recommended dose of nivolumab is 480 mg every 4 weeks (Q4W) over 30 minutes infusion. This dose was recently approved in the United States for the adjuvant treatment of high-risk melanoma patients.

4.4. End of Study Definition

A subject is considered to have completed the study if he/she has completed all phases of the study including the end of study (EOS) visit.

The end of the study is defined as the date of the last survival contact of the last subject in the study.

5. STUDY POPULATION

Prospective approval of protocol deviations to recruitment and enrollment criteria, also known as protocol waivers or exemptions, is not permitted.

5.1. Inclusion Criteria

Subjects are eligible to be included in the study only if all of the following criteria apply:

Age

1. Subject must be ≥ 18 years of age inclusive, at the time of signing the informed consent.

Type of Subject and Disease Characteristics

2. Histologic diagnosis of melanoma belonging to the following American Joint Committee on Cancer (AJCC) 8th edition TNM stages (Tx or T1-4) and (N1b, N1c, N2b, N2c, N3b or N3c) and/or (M1a)
3. Must be considered surgically operable and may present as any of the following groups:
 - a. Primary melanoma with clinically apparent regional lymph node metastases, confirmed by pathological diagnosis.
 - b. Clinically detected recurrence of melanoma at regional lymph node basin(s), confirmed by pathological diagnosis.
 - c. Clinically or histologically detected primary melanoma involving multiple regional nodal groups, confirmed by pathological diagnosis.
 - d. Clinically detected single site of nodal metastatic melanoma arising from an unknown primary, confirmed by pathological diagnosis.
 - e. Subjects with in transit or satellite metastases with or without lymph node involvement are allowed if they are considered surgically resectable at Screening by the treating surgical oncologist.
 - f. Subjects with distant cutaneous/subcutaneous, soft tissue or nodal metastases with or without regional lymph node involvement are allowed if they are considered potentially surgically resectable and can be biopsied at Screening by the treating surgical oncologist. Elevated LDH is not an exclusion.
4. Subjects are eligible for this study either at presentation for primary melanoma with concurrent regional nodal and/or in-transit or distant metastasis, or at the time of clinically detected nodal, in transit, or distant recurrence.
5. Subjects must be evaluated by standard-of-care full body imaging studies including positron emission tomography – computed tomography (PET-CT ;preferred; including diagnostic CT component if possible) or CT (if PET-CT cannot be done) as well as magnetic resonance imaging (MRI) of the brain (or CT if MRI cannot be done) as part of the initial clinical work-up at Screening (no more than 4 weeks prior to Cycle 1, Day 1).
6. Have measurable disease based on RECIST v1.1, with at least one anatomically distinct lesion. Lesion or lesions must meet all the following baseline criteria:
 - a. Accessible for electroporation

- b. Must be measured in at least one dimension (longest diameter in the plane of measurement is to be recorded)
- c. Greater than 3 mm

Sex**7. Male and Female**

Contraceptive use by men or women should be consistent with local regulations regarding the methods of contraception for those participating in clinical studies.

- a. Male subjects:

Male subjects of childbearing potential must be surgically sterile, or must agree to use adequate method of contraception during the study and at least 5 months following the last day of study drug administration.

Note: Abstinence is acceptable if this is the usual lifestyle and preferred contraception for the subject

- b. Female subjects:

Women of childbearing potential must have negative serum or urine pregnancy test within 72 hours prior to receiving the first study drug administration. If the urine test is positive or cannot be confirmed as negative, a serum pregnancy test will be required.

For women of childbearing potential, must be willing to use an adequate method of contraception from 30 days prior to the first study drug administration and 5 months following last day study drug administration (either tavo or nivolumab); acceptable methods include hormonal contraception (oral contraceptives – as long as on stable dose, patch, implant, and injection), intrauterine devices, or double barrier methods (e.g. vaginal diaphragm/vaginal sponge plus condom, or condom plus spermicidal jelly), sexual abstinence or a vasectomized partner. Women may be surgically sterile or at least 1-year post-last menstrual period.

Note: Abstinence is acceptable if this is the usual lifestyle and preferred contraception for the subject.

Informed Consent**8. Capable of giving signed informed consent which includes compliance with the requirements and restrictions listed in the informed consent form (ICF) and in this protocol****5.2. Exclusion Criteria**

Subjects are excluded from the study if any of the following criteria apply:

Medical Conditions

1. Subject has a known additional malignancy that is progressing or requires active treatment. Exceptions include basal cell carcinoma of the skin, squamous cell carcinoma of the skin that has undergone potentially curative therapy or in situ cervical cancer. Also,

includes patients who are considered disease-free for at least 3 years from the last definitive treatment for a second malignancy.

2. Subjects who have Human Immunodeficiency Virus (HIV) (HIV 1/2 antibodies at Screening). HIV testing at screening is not required unless considered clinically indicated by the treating physician.
3. Subjects who have active Hepatitis B (e.g., HBsAg reactive) or Hepatitis C (e.g., HCV RNA [qualitative] is detected at Screening); *Note: Subjects who have been vaccinated against Hepatitis B and who are positive only for the Hepatitis B surface antibody are permitted to participate in the study.* Hepatitis B and C testing at screening is not required unless considered clinically indicated by the treating physician.
4. Subject has a diagnosis of immunodeficiency or is receiving systemic steroid therapy or any other form of immunosuppressive therapy within 7 days prior to the first dose of study drug. The use of physiologic doses of corticosteroids may be approved after consultation with the Principal Investigator.
5. Subject has a history of (non-infectious) pneumonitis that required steroids or current pneumonitis.
6. Subject has a history of interstitial lung disease.
7. Subject has an active infection requiring systemic therapy.
8. Subject has a history or current evidence of any condition, therapy, or laboratory abnormality that might confound the results of the trial, interfere with the subject's participation for the full duration of the trial, or is not in the best interest of the subject to participate, in the opinion of the treating investigator.
9. Subject has not recovered (i.e., > Grade 1 at Cycle 1, Day 1) from AEs due to a previously administered agent.

Note: Subjects with \leq Grade 2 neuropathy or \leq Grade 2 alopecia are an exception to this criterion and may qualify for the study.

Note: If subject underwent major surgery or radiation therapy of >30 Gy, they must have recovered adequately from the toxicity and/or complications from the intervention prior to starting study combination therapy.

10. Subject has known psychiatric or substance abuse disorders that would interfere with cooperation with the requirements of the study.
11. Subjects who are pregnant or breast feeding or expecting to conceive or father children within the projected duration of the trial, starting with the screening visit through 5 months after the last dose of trial treatment.

Prior/Concomitant Therapy

12. Subjects with electronic pacemakers or defibrillators

13. Subjects who have received a live-virus vaccination within 30 days of the first dose of treatment. Seasonal flu vaccines that do not contain live virus are permitted
14. Subjects who have received transfusion of blood products (including platelets or red blood cells) or administration of colony stimulating factors (including G-CSF, GM-CSF or recombinant erythropoietin) within 4 weeks prior to study Cycle 1, Day 1.
15. Previous treatment with anti-PD1 or anti-PDL1 immunotherapy.

Prior/Concurrent Clinical Study Experience

16. Participation in another clinical study and systemic therapy within 30 days of Cycle 1, Day 1.

Note: Subjects participating in an observational study are an exception to this criterion and may qualify for the study with Principal Investigator approval.

Organ Function Assessments

17. ECOG Performance Status: >1
18. Inadequate organ function as defined below. All screening laboratories should be performed within 10 days of treatment initiation.

System	Laboratory Value
Hematological	
Absolute neutrophil count (ANC)	$<1.5 \times 10^9/\text{L}$
Platelets	$<100 \times 10^9/\text{L}$
Hemoglobin	$<9 \text{ g/dL}$ or $<5.6 \text{ mmol/L}$
Renal	
Creatinine* OR	$>1.5 \times$ the upper limit of normal (ULN) OR
Measured or calculated creatinine clearance (CrCl)	$\geq 60 \text{ mL/min}$ for subject with creatinine levels $\leq 1.5 \times$ institutional ULN
Glomerular filtration rate (GFR) can also be used instead of creatinine or CrCl	
Hepatic	
Total bilirubin	$>1.5 \times$ ULN OR direct bilirubin $>$ ULN for subjects with total bilirubin levels $\leq 1.5 \times$ ULN
Aspartate aminotransferase (AST) and alanine aminotransferase (ALT)	$>2.5 \times$ ULN OR $>5 \times$ ULN for subjects with liver metastases
Coagulation [¥]	

International Normalized Ratio (INR) or Prothrombin Time (PT)	>1.5 × ULN unless subject is receiving anticoagulant therapy as long as PT or PTT is within therapeutic range of intended use of anticoagulants
Activated Partial Thromboplastin Time (aPTT)	

* Creatinine clearance should be calculated per institutional standard.
 
PT, INR and PTT will be done only if considered clinically indicated by the treating physician.
	

Other Exclusions

19. Subject has severe hypersensitivity (\geq Grade 3) to nivolumab and/or any of its excipients

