7. CBC w/differential to include: Hemoglobin, Platelets, Red Blood Cell, White Blood Cell, Basophils (Absolute; Abs), Eosinophils (Abs), Lymphocytes (Abs), Monocytes (Abs), Neutrophils (Abs) and Hematocrit.
8. Serum Chemistry to include: sodium, potassium, CO_2 or bicarbonate, chloride, albumin, alkaline phosphatase, alanine aminotransferase (ALT), aspartate aminotransferase (AST), lactate dehydrogenase (LDH), total bilirubin, blood urea nitrogen (BUN), calcium, creatinine, non-fasting glucose, magnesium, phosphorus, and total protein, serum chemistry and hematology do not need to be repeated if the Screening evaluations occurred within 10 days of the C1D1, unless a clinically significant change in the interim is suspected.
9. Thyroid function will include free T3, FT4 and TSH (will not need to be re-tested at C1D1 if screening evaluations were done within 10 days of C1D1).
10. Virology including HIV 1/2 antibodies, HBsAg, HCV RNA (qualitative). Also, PT, PTT. These tests will be done only if considered clinically indicated by the treating physician.
11. Only if considered clinically indicated by the treating physician and only for women of childbearing potential (i.e., postmenopausal women and women who have had a hysterectomy, oophorectomy are not of child- bearing potential). Local urine test must be performed within 72 hours prior to first study treatment and if positive, a serum test s required. An EOS urine pregnancy test will be performed and if positive, a serum test will be done.
12. Urinalysis will be done only if clinically indicated.
13. Tumor imaging will be performed in accordance with the standard of care as determined by the treating physician(s) and ideally should be done with the same imaging technique (computed tomography [CT] or magnetic resonance imaging [MRI]; PET-CT preferred including diagnostic CT component if possible) to be used in a given subject throughout the study.

Baseline MRI brain is required to rule out metastatic disease if determined to be clinically indicated by the treating physician(s). CT should include the chest, abdomen and pelvis (and head and neck and all extremities if clinically indicated due to metastatic lesions or lymphadenopathy). All imaging will be assessed locally by the Investigator.

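### The creatinine-clearance row of exclusion item 18 is printed in the adequate-function direction, so where it is applied it excludes normal clearance and passes CrCl below 60 mL/min; screening on creatinine alone is unaffected.

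*Combined protocol and SAP*

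**What the plan says.** Section 5.2 opens with "Subjects are excluded from the study if any of the following criteria apply", and item 18 is headed "Inadequate organ function as defined below". Any value listed in the table is therefore an excluding value.

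The renal block has three lines:

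- Creatinine above 1.5 × ULN, joined by OR to the next line.
- Measured or calculated CrCl: "\geq 60 \text{ mL/min}$ for subject with creatinine levels $\leq 1.5 \times$ institutional ULN".
- A line with no cut-off of its own: "Glomerular filtration rate (GFR) can also be used instead of creatinine or CrCl".

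A table footnote adds "Creatinine clearance should be calculated per institutional standard". The required chemistry panel in the Schedule of Activities (Section 1.3, note 8) includes "blood urea nitrogen (BUN), calcium, creatinine, non-fasting glucose, magnesium, phosphorus, and total protein" but does not name CrCl. Table 4 in Appendix 2 (Section 10.2) likewise lists creatinine and neither CrCl nor GFR. No other section states or corrects a CrCl cut-off.

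**The concern.** A table of excluding values should show the abnormal range in every row. The CrCl row shows the normal range. Read literally, it turns away subjects whose kidneys work well and lets through those with reduced clearance, provided their creatinine is not above 1.5 × ULN. That contradicts the item's own heading.

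Two things are at stake. One is the safety intent of the renal criterion at any site that calculated clearance. The other is the later classification of eligibility violations in the disposition summary (Section 9.4.1), where the printed row would flag the wrong subjects.

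**Working it through.** The plan derives no figure from this row, so the check is one of direction and then of classification.

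**Direction of each row with a printed threshold (Section 5.2, item 18)**

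| Row | Printed value | Direction |
|---|---|---|
| ANC | <1.5 × 10⁹/L | abnormal |
| Platelets | <100 × 10⁹/L | abnormal |
| Hemoglobin | <9 g/dL | abnormal |
| Creatinine | >1.5 × ULN | abnormal |
| CrCl | ≥60 mL/min, if creatinine ≤1.5 × ULN | **adequate** |
| Total bilirubin | >1.5 × ULN, or direct bilirubin >ULN if total ≤1.5 × ULN | abnormal |
| AST/ALT | >2.5 × ULN (>5 × ULN with liver metastases) | abnormal |
| INR/PT | >1.5 × ULN | abnormal |

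Seven rows point one way and one points the other. The bilirubin row is the closest comparison because it has the same two-part form: its second limb excludes direct bilirubin above "ULN for subjects with total bilirubin levels" no higher than 1.5 × ULN. That limb is in the abnormal direction.

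**Classification.** Let Cr be creatinine in multiples of ULN.

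- Creatinine only: exclude if Cr > 1.5.
- Both rows as printed: exclude if Cr > 1.5, or if Cr ≤ 1.5 and CrCl ≥ 60.
- Both rows, sign reversed: exclude if Cr > 1.5, or if Cr ≤ 1.5 and CrCl < 60.

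| Cr (× ULN) | CrCl (mL/min) | Creatinine only | Both rows, printed | Both rows, sign reversed |
|---|---|---|---|---|
| 1.0 or 1.5 | 45 or 59 | pass | pass | exclude |
| 1.0 or 1.5 | 60 or 90 | pass | exclude | pass |
| 1.6 | any of 45, 59, 60, 90 | exclude | exclude | exclude |

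The printed row gives the wrong answer throughout the subgroup it defines (Cr ≤ 1.5). No reading of OR repairs this, because the reversal lies within the row. Creatinine-only screening gives the same result before and after the correction.

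**Design figures.** With X₁ ~ Bin(22, p) and X₂ ~ Bin(11, p), the probability of declaring the therapy worth pursuing is the sum over x from 3 to 22 of P(X₁ = x) × P(X₂ ≥ 7 − x). At p = 0.10 this is 0.0409, within the stated 0.05. At p = 0.30 it is 0.9018, against the stated 90%. No renal threshold enters the formula.

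**The case against.** The strongest reply is that nothing live depends on the row. Creatinine OR CrCl, with GFR as a further substitute, lets a site avoid it. The required panels name creatinine and not clearance. Creatinine above 1.5 × ULN and the general exclusion in item 8 still screen renal function. A July 2023 note in Section 1.3 records that all patients are past the neoadjuvant phase. All of this stands and limits the consequence. It does not make the row correct, and the footnote on calculating clearance shows that CrCl is a usable route.

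A second reply is that more than the sign may be wrong. CrCl may have been meant as a rescue for raised creatinine, excluding only when creatinine exceeds 1.5 × ULN and clearance is below 60. Admitting creatinine ≤1.5 × ULN with CrCl below 60 would then be no error. This is possible, but the row would still need changing, and the reading fits the printed qualifier and the bilirubin row less well. It is the reason to check intent first.

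A reader might go further than the documents allow in three ways:

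- **That patients with normal kidneys were turned away, or patients with impaired kidneys enrolled.** No screening data are given, and neither the test used nor the checklist wording is shown.
- **That a site was bound to the misprint because "Prospective approval of protocol deviations to recruitment and enrollment criteria, also known as protocol waivers or exemptions, is not permitted".** That sentence bars case-by-case waivers. It does not bar an approved amendment (Section 10.1.1), and the table itself offers other tests.
- **That treated subjects with CrCl below 60 should now be listed as violations.** Those validly screened on creatinine or GFR alone met the criterion as written.

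A misread symbol in the text extraction cannot be wholly excluded, though the row is intact and legible.

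**Conclusion.** The CrCl threshold is wrong as written, and the severity is minor. One of eight printed thresholds is reversed. The error acts only where that row is applied, and only for creatinine at or below 1.5 × ULN. The number of subjects affected cannot be derived from the documents.

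A reader might infer that the efficacy result is compromised. It is not: the primary analysis (Section 9.4.3) uses every enrolled subject who received at least one dose of either agent (Section 9.3), whatever their clearance. The pCR estimate, type I error, power and stage decisions are unaffected, and no future enrolment decision changes.

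The conclusion that the row is wrong rests on the inequality being as supplied and on the table listing excluding values, as its heading says. The exact wording of the correction also assumes that the qualifier on creatinine was intended as printed.

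**What to change.** First confirm the intent, including the qualifier, against the eligibility checklist used for registration (Section 5.4). Then change the CrCl row to: <60 mL/min for subjects with creatinine ≤1.5 × institutional ULN. This matches the item heading and the form of the bilirubin row.

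When eligibility violations are reported under Section 9.4.1, do not flag subjects with CrCl of 60 mL/min or more on account of the misprint. Do not retroactively flag subjects who were validly screened on creatinine or GFR alone.

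The cost is one symbol in one table cell at the next amendment, plus a look at the checklist. No patients, procedures or data are added.
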